11.4 Demographics and Baseline Characteristics

Patient characteristics will include the following:

- Patient demographics (age, gender, race, ethnicity)
- Baseline disease characteristics (number and size of baseline target tumors, baseline Child Pugh stage, ECOG performance status, unilobar or bilobar disease)

- Clinically significant medical history
- Concurrent medical conditions
- Prior cancer therapies

11.5 Efficacy Analysis

11.5.1 Median Overall Survival

The primary efficacy analysis of median overall survival will be performed on the ITT population when the last patient has completed two years of follow-up after their first study TACE procedure or 218 deaths have been observed in the two groups combined, whichever comes first. Patients will be followed for survival until death or loss to follow up. Overall survival time will be calculated in months from the date of the first study TACE embolization to the date of death or date last known to be alive for patients who are lost to follow up. Median overall survival time will be calculated for each treatment group using the Kaplan-Meier (product-limit) method and corresponding 95% confidence intervals will be generated. Treatment groups will be compared on median survival using a log-rank test.

One and two year survival rates and corresponding 95% confidence intervals will also be calculated for both treatment groups. Survival analyses will also be performed for the Evaluable population.

In order to assess the consistency of observed treatment effect across investigational sites, a data poolability analysis will be performed on the primary efficacy outcome of overall survival using the ITT population. Median overall survival data will be summarized by site, including Kaplan-Meier plots. In addition, a Cox proportional hazards model will be run including factors for treatment group, investigational site, and an interaction term for treatment group and investigational site. For purposes of this analysis, sites enrolling fewer than 10 patients may be pooled into a single site.

A multivariate analysis of the primary efficacy outcome of overall survival will be performed using a Cox proportional hazards model for the ITT population. This analysis will be considered supportive only. The model will include factors for site, as well as all variables included in the final adaptive randomization model. In addition, key baseline factors found to be significantly different between the two treatment groups at baseline will also be evaluated in the model.

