This is a phase 3, multicenter, randomized, controlled study designed to evaluate the safety and effectiveness of treating patients with localized, non resectable hepatocellular carcinoma with conventional transarterial chemoembolization (cTACE) or HepaSphere/QuadraSphere transarterial chemoembolization (hqTACE).

The study will consist of a screening period in which patient eligibility will be determined. Patients meeting the study entry criteria will be randomized on a 1:1 basis to receive either cTACE or hqTACE. A TACE cycle is defined as a single embolization for patients with unilobar disease and an embolization of each lobe for patients with bilobar disease. Patients will receive up to 3 TACE cycles. The first embolization will be done within 4 weeks of baseline imaging, and the second and third TACE cycles will take place 8 and 16 weeks after the first TACE cycle, respectively. MRIs will be done 4 weeks after each TACE cycle to determine tumor response and will be assessed by Central Reviewers.

The primary study endpoint will be overall survival. Study treatment will end after a maximum of 3 TACE cycles. Patient survival will be followed from date of first study TACE procedure until a date of death is obtained or the patient is lost to follow-up. Treatments for hepatocellular carcinoma after the study TACE treatments are complete will be documented during the survival period to the extent possible.

For cTACE, 75 mg/m^2 of doxorubicin (maximum dose of 150mg of doxorubicin per TACE cycle) mixed with ethiodized oil will be delivered into the hepatic artery via microcatheter, and then the artery will be occluded with particle PVA. For the hqTACE, the 75 mg/m^2 of doxorubicin (maximum dose of 150mg of doxorubicin per TACE cycle) will be loaded onto the HepaSphere/QuadraSphere Microspheres (through ionic bonding when the spheres are exposed to doxorubicin solubilized in normal saline) and delivered via microcatheter. No ethiodized oil is used with the microspheres. Dosage will be calculated and rounded up to the nearest 25 mg of doxorubicin. The occlusion endpoint will be stasis to the second or third branches. If stasis has not been reached when the target dosage of doxorubicin has been delivered, additional bland embolic (particle PVA for the cTACE arm and HepaSphere/QuadraSphere for the hqTACE arm) will be used to achieve a consistent endpoint.

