7.9 Survival follow -up

Patients will be followed from date of first embolization of the first cycle until a date of death is obtained or the patient is lost to follow up. Survival contacts will be attempted every 3 months after completion of final protocol-specified study visit. Contacts may be by visit, telephone, email, or written response, and may be obtained from the patient, medical records, or care givers/family members. Patients may undergo further treatment after the study-specified TACE treatments at the discretion of their physicians, including but not limited to transplant, resection, percutaneous ethanol injection (PEI), radiofrequency ablation (RFA), additional

embolizations, sorafenib or other treatments, including other investigational methods. Patients who have additional embolizations after the three protocol-defined TACE cycles must have the same type of embolization (cTACE or hqTACE) they received during the study. It would be unethical to deny these patients further treatment which might provide benefit, but any and all of the above could affect long term survival and be confounds in the analysis and interpretation of this study data. For this reason treatments and outcomes after the final study TACE will be documented, to the extent possible, during the survival follow-up period, but will not be considered safety or efficacy outcomes in this study, except time to untreatable progression (TTUP). Survival and TTUP will be the only outcomes evaluated after completion of the protocol specified treatment phase of the investigation.

7. Withdrawal of Patients

Patients will be informed that they have the right to withdraw from the study at any time for any reason, without prejudice to their medical care. The investigator also has the right to withdraw patients from the study for any of the following reasons:

- Adverse events, including cardiac ejection fraction <50%
- Progression to extrahepatic disease
- Refusal of treatment
- Patient request
- Inability to complete study procedures
- Lost to follow up
- Non compliance with study requirements

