11.3 Analysis Populations

11.3.1 Safety Population (SAF)

All randomized patients who have at least one TACE procedure will be included in the Safety Population.

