11.3.2 Intent-to-Treat Population (ITT)

The Intent- to-Treat (ITT) Population is defined as all patients randomized in the study, regardless of treatment status. This will be the primary population for the efficacy analyses.

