11.3.3 Evaluable Population (EVAL)

All randomized patients who have at least one TACE procedure and who have at least one post-baseline tumor evaluation and who do not have any major protocol violations will be included in the Evaluable Population.

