11.5.2 Objective Response Rate

A secondary efficacy outcome is the Objective Response Rate (ORR). For purposes of this analysis tumor response will be based on the last post TACE liver MRI response recorded for each patient, as determined by the Central Reviewers based on mRECIST criteria. The ORR will be calculated for the ITT Population as the number of patients with a confirmed complete or partial response (based on mRECIST criteria) divided by the number of ITT patients [ORR=(# CR + # PR)/total # patients]. Patients who have discontinued from the study prior to their first post

baseline tumor evaluation will be considered to have progressed for purposes of calculating the ORR for the ITT population. Ninety-five percent confidence intervals will be calculated for the ORR for both treatment groups and for the difference between treatments. The ORR and corresponding 95% confidence intervals will also be calculated for the Evaluable Population. The ORR efficacy analysis will be performed on a locked database that will be unblinded only after all patients have completed the protocol specified treatment phase of the investigation. Treatment comparisons of the ORRs will be performed using Fisher's Exact Test.

In order to assess the robustness of the ORR analysis using the last post TACE MRI response, a sensitivity analysis of the ORR data using the first post TACE MRI response for the ITT population will be performed. In addition, a data poolability analysis will be performed using a multiple logistic regression model including factors for treatment group, investigational site, and an interaction term for treatment group and investigational site for the ITT population. For purposes of this analysis, sites enrolling fewer than 10 patients may be pooled into a single site.

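### Overall survival starts at the first TACE, but the primary population is all randomized patients, so a patient randomized and never embolized has no defined survival time

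*Combined protocol and SAP*

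**What the plan says.** The primary efficacy analysis of overall survival (Section 11.5.1) is on the ITT population, which Section 11.3.2 gives as "defined as all patients randomized in the study, regardless of treatment status".

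The clock starts at treatment:
- Survival time (Section 11.5.1): "Overall survival time will be calculated in months from the date of the first study TACE embolization to the date of death", or to the date last known alive for patients lost to follow-up.
- Analysis timing (Section 11.5.1): "when the last patient has completed two years of follow-up after their first study TACE procedure", or at 218 deaths if that comes first.
- Follow-up (Section 5): "Patient survival will be followed from date of first study TACE procedure".
- Follow-up (Section 7.9): "Patients will be followed from date of first embolization of the first cycle". Footnote 3 of the Schedule of Procedures in Appendix A uses the same start.

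Other parts of the plan recognise that some randomized patients may not be treated. Section 11.3.1: "All randomized patients who have at least one TACE procedure will be included in the Safety Population". Section 11.3.3: "All randomized patients who have at least one TACE procedure and who have at least one post-baseline tumor evaluation", with a further condition on protocol violations. For objective response, Section 11.5.2 has a rule for ITT patients who leave before any post-treatment scan; it ends "baseline tumor evaluation will be considered to have progressed for purposes of calculating the ORR for the ITT population". Section 11.5.1 has no matching rule for survival.

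Randomization takes place within one week of the scheduled first TACE (Section 6), preferably on the same day (Appendix A, footnote 8). The treating radiologist cannot be blinded (Section 6).

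**The concern.** For the primary endpoint, the stated time origin cannot be applied to every member of the stated population. A patient randomized and never embolized belongs to ITT but has no start date, and no censoring rule or exclusion fills the gap.

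If analysts applied the rule literally, that patient would have no survival time and would drop out of the analysis. The cause would be something that happened after randomization, under an operator who knows the arm. If the arms differed in how many patients went untreated, and those patients had a worse prognosis, the comparison would lean towards the arm that lost more of them.

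The documents suggest how such patients could arise. Exclusion criterion u covers hepatofugal flow and shunts that cannot be closed. The screening list in Section 7.1 contains no arteriography, while Appendices C and E place diagnostic angiography at the start of the TACE procedure, after randomization. Discovery at that point is plausible, but this is an inference and no rate is given.

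The calendar trigger has the same gap if the last randomized patient is never embolized. So does time to untreatable progression (Section 11.5.6): both its origin and its censoring rule for patients without a scan refer to the first TACE.

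**Working it through.** **1. The plan's own figure.** Inputs (Section 11.2): hazard ratio 1.5, two-sided 5%, 85% power, 1:1 allocation. Schoenfeld's formula:

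D = 4(1.960 + 1.036)² / (ln 1.5)² = 218.4

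This matches the 218 deaths in Section 11.5.1. Power at 218 deaths is Φ(√218 × 0.4055 / 2 − 1.960) = Φ(1.033) = 84.9%. The formula depends on deaths and not on the time origin, so the target stays the same if survival is timed from randomization.

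**2. Number of patients.** 255 × 2 = 510 are randomized. The assumed untreated rates of 1%, 2% and 5% give 5.1, 10.2 and 25.5 patients.

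**3. Type I error if untreated patients are dropped.** Null simulation, 20,000 runs per cell, Monte Carlo standard error about 0.15 to 0.2 points. Assumptions: 510 patients, uniform accrual over 30 months, 20-month median, 10% of patients frail at the stated hazard multiple, all untreated patients frail, cut-off at the 218th death among all randomized patients or 24 months after last accrual.

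| Split of untreated by arm | Hazard multiple | 1% | 2% | 5% |
|---|---|---|---|---|
| 50/50 | 1, 1.5 and 3 | 4.78–5.29% over all nine cells | | |
| 65/35 | 3 | 5.15% | 5.15% | 5.73% |
| 80/20 | 1 | 4.78% | 5.01% | 4.87% |
| 80/20 | 1.5 | 4.81% | 5.27% | 5.03% |
| 80/20 | 3 | 5.08% | 5.59% | 7.87% |

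Smaller repeat simulations of the 5%, 80/20, threefold cell gave 7.3% and 7.4%, hence about 7 to 8%. One repeat gave 4.7% and 4.5% at 1% and 2% untreated, so there is no clear overall inflation at those rates. At 80/20 and threefold hazard, false positives favouring the arm with more untreated patients were 3.1%, 4.0% and 7.2% (nominal 2.5%). The log-rank test on all randomized patients stayed at 4.6 to 5.3% in all 27 cells.

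**4. Power when all randomized patients are analysed.** If untreated patients gain no benefit, a first approximation multiplies ln 1.5 by (1 − untreated share):
- 1%: Φ(2.993 × 0.99 − 1.960) = 84.2%
- 2%: Φ(2.993 × 0.98 − 1.960) = 83.5%
- 5%: Φ(2.993 × 0.95 − 1.960) = 81.2%

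Simulation (40,000 runs per cell, medians 16 and 24 months) gave 84.5% with none untreated. With untreated patients at the cTACE hazard it gave 83.8%, 82.7% and 80.6%; at three times that hazard, 83.6%, 82.0% and 78.5%. Dropping them at the cTACE hazard gave 84.1%, 83.4% and 82.6%.

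**5. Shift for treated patients.** One week is 7 / 30.44 = 0.23 months, the most that survival times lengthen if TACE takes place as scheduled.

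**The case against.** A reader might infer that the plan makes the primary analysis a treated-patient analysis. The documents do not support that. Sections 11.3.2 and 11.5.1 keep untreated patients in ITT, so dropping them would breach stated text. What is missing is a start date. The type I figures above therefore describe one possible handling of the gap, which the plan does not prescribe.

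A reader might also infer material bias. The documents give no untreated rate, no imbalance between arms and no prognosis for such patients. Eligibility is settled before randomization and TACE follows within a week, so few are expected. Withdrawn patients are asked to consent to survival contact (Withdrawal of Patients), so an end date will often be obtainable.

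A third inference is that the rule will be chosen after unblinding. Section 6 has survival collection continue unblinded after the treatment-phase lock, so this could happen, but nothing provides for it.

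Finally, a narrower repair is available: use the randomization date only for patients with no TACE. That would close the gap without touching treated patients. It would, however, put two time origins in one survival curve, whereas randomization is available for everyone and moves treated patients by about a week at most.

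These arguments limit the size of the problem. None of them supplies the missing start date.

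**Conclusion.** The point holds as an inconsistency of definition in the primary endpoint that should be fixed. The origin rule of Section 11.5.1 cannot be applied to the whole population of Section 11.3.2, and the plan itself allows for the patients it misses.

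The likely numerical effect is small. Over assumed untreated rates of 1 to 5%, literal application of the rule leaves type I error near 5% with an equal split or similar hazards. An error of about 7 to 8% requires 5% untreated, an 80/20 split and a threefold hazard together, none of which the documents suggest. The case for the change is that the primary analysis should be fully defined in advance and the remedy is cheap; it does not rest on a large expected bias.

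**What to change.** In Section 11.5.1, define overall survival as the time from randomization to death from any cause, for all randomized patients in the arm assigned, with patients not known to have died censored at the date last known alive. State that the 218 deaths are counted among all randomized patients, and run the two-year trigger from randomization. Align the survival start date in Sections 5 and 7.9 and in Appendix A, footnote 3. Add to Section 7.9 that randomized patients who receive no TACE are followed for survival every 3 months from randomization, subject to consent. Keep survival from first TACE in the Safety Population as a sensitivity analysis.

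For time to untreatable progression, a tertiary outcome, use randomization as the origin. Censor never-embolized patients without documented untreatable progression at the last date known to be free of it, which is the general rule already in Section 11.5.6. They should not be censored at randomization: that would remove them from the log-rank test while those who progress still counted as events.

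The cost is a contact schedule for a few untreated patients, because contacts now begin only after the final protocol visit, and a small loss of power: about 84% at 1% untreated and about 81% at 5% if they gain no benefit, or about 78% at 5% if they also die at three times the hazard.

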Hepatocellular carcinoma is the fifth most common cancer, the third most common cause of cancer death worldwide, and results in over 600,000 mortalities each year (Bosch 2004). In 2010 it is estimated there will be more than 23,000 new cases diagnosed in the United States, with over 18,000 deaths (ACS 2009). Incidence in the US is expected to increase 59% between 2010 and 2030 (Smith 2008), primarily due to a rise in hepatitis B and hepatitis C infections. Three year survival for patients with unresectable hepatocarcinoma is only 10-40% (Llovet 2003), and the five year survival rate for all stages combined is less than 10% (ACS 2009). The primary reason for such poor prognosis is that liver cancer patients have underlying hepatic disease which can itself be fatal and can impact treatment options and response.

b. Treatment of Hepatocellular Carcinoma

The only potentially curative treatment for hepatocellular carcinoma is liver transplantation or tumor resection. However, only about 25% of liver cancers are diagnosed when they can be treated surgically. For patients with intermediate stage hepatocellular cancer, chemoembolization is often the best option.

Tumor directed hepatic artery embolization is possible because normal liver tissue receives most of its blood supply from the portal vein, while hepatocellular tumors derive most of their flow from the hepatic artery (Breedis 1954; Kan 1993). Transarterial chemoembolization (TACE) combines the local delivery of chemotherapy with induction of tumor ischemia through occlusion of feeding vessels. TACE has the dual benefit of focusing treatment on the lesions and reducing the adverse effects of systemic exposure to chemotherapy.

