- e. Patient MUST meet at least ONE of the following criteria:
 - i. Stage Child-Pugh B 7
 - ii. Recurrent HCC
 - iii. Performance status ECOG 1
- f. Patient has a life expectancy of at least 6 months
- g. Absence of occlusive thrombus to the main portal trunk

4. Exclusion Criteria

If patients meet any of the following criteria they may not be entered into the study:

- a. Current or previous treatment with chemo- or radiation therapy or sorafenib
- b. Previous treatment with any form of transarterial embolization for HCC
- c. Patients with current or history of any other cancer except non-melanomatous skin cancer
- d. Female patients who are pregnant, breastfeeding, or premenopausal and not using an effective method of contraceptive
- e. Performance status ECOG ≥ 2
- f. Child-Pugh scores >7
- g. Active gastrointestinal bleeding
- h. Evidence of uncorrectable bleeding diathesis
- i. Extrahepatic spread of the HCC
- j. Total Bilirubin ≥ 3 mg/dL
- k. $>50\%$ tumor involvement of the liver
- l. Infiltrative or diffuse HCC
- m. Encephalopathy not adequately controlled medically
- n. Presence of ascites not controlled medically
- o. Presence of medically relevant localized or systemic infection, other than hepatitis B, C, D, E or G
- p. Any contraindication for MRI (eg metallic implants)
- q. Allergy to contrast media that cannot be managed with prophylaxis
- r. Allergy to iodized oil
- s. Any contraindication to arteriography
- t. Any contraindication for doxorubicin administration, including the following:
 - i. White Blood Cell count (WBC) <3000 cells/mm³
 - ii. Absolute Neutrophil <1500 cells/mm³
 - iii. Cardiac ejection fraction $<50\%$
 - iv. Other condition deemed exclusionary by physician
- u. Any contraindication for hepatic embolization, including the following:
 - i. Porto-systemic shunt, or an arteriovenous shunt that cannot be adequately closed prior to chemoembolization
 - ii. Hepatofugal blood flow
 - iii. Serum creatinine > 2 mg/dL
 - iv. Uncorrectable impaired clotting
 1. Platelet $< 50,000$ /mm³
 2. International Normalized Ratio (INR) > 1.4
 3. Activated Prothrombin Time (aPTT) less than 21 or greater than 40

- v. $AST \geq 5X$ upper limit of normal for lab
- vi. $ALT \geq 5X$ upper limit of normal for lab
- vii. Severe peripheral vascular disease
- viii. Other condition deemed exclusionary by physician

5. Study Design

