The study will evaluate safety throughout the protocol specified treatment phase of the investigation by assessing adverse events, as well as clinically significant changes from baseline in laboratory values, findings on physical examination including vital signs, ECOG performance

status, and cardiac ejection fraction testing. Concomitant medication usage will also be assessed. Blood samples will be drawn for pharmacokinetic evaluation the morning after the first TACE procedure and at the time of the MRI and laboratory evaluations following the first TACE cycle. In addition, patients who are still hospitalized at least 6 hours following the first PK blood sample collection will have an additional PK blood sample drawn.

6. Randomization and Blinding

Randomization and blinding of treatment identification will be used to reduce potential bias during data collection and evaluation of clinical endpoints. The treatment assignments will be unblinded once all data from the protocol specified treatment phase has been entered into the clinical database, all of the necessary standard data cleaning techniques have been implemented, and the database has been locked.

Once the informed consent has been signed and the patient has met all the study entry criteria, the patient will be considered eligible for randomization. Patients will be randomized to either the cTACE or hqTACE treatment groups in a 1:1 ratio within 1 week of their first scheduled TACE. Randomization schedules will be generated using an adaptive randomization model (based on the algorithm developed by Simon and Pocock). The adaptive model will control the balance of treatment groups within each site and also take into account the following baseline factors which will be weighted based on importance: Child-Pugh Stage (A or B), ECOG performance (0 or 1) status, recurrent disease (yes or no), AFP (<400 ng/mL or ≥400 ng/mL), presence of macrovascular invasion (yes or no), and tumor location (unilobar or bilobar).

Patients will be blinded to the treatment group to which they are assigned. In order to minimize any bias in interpretation of tumor response, the Central Reviewers who assess treatment response will also be blinded to which treatment the patient is receiving. It is not possible for treating radiologists to be blinded to treatment group because the method of embolization is different for the 2 methods of TACE. The primary efficacy outcome of overall survival is unaffected by blinding.

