In an effort to assess the level of patient blinding, per FDA recommendation, patients will be asked the following question after they have completed their protocol specified embolizations: *“What treatment do you think you received?”* with response options of cTACE, hqTACE, or Unknown. This data is informative in nature and will not have any influence on the analyses of the study outcomes.

The study will be unblinded once all of the patients have received up to three study TACE cycles and follow up study procedures (protocol specified treatment phase of the investigation) and the database has been cleaned and locked. Unblinded survival data collection will continue until all patients have died or been lost to follow-up.

Treatment and Assessment

Study patients will be randomized to receive hqTACE or cTACE, with a target dose of $75\text{mg}/\text{m}^2$ of doxorubicin for each TACE cycle (maximum dose of 150mg of doxorubicin per TACE cycle). Up to a total of 3 TACE cycles will be administered to each patient within approximately a 6 month period from initial treatment, based on response as determined by Central Reviewers, using mRECIST. See Study Flow Charts, Appendix A.

Taking windows for second and third TACE cycles into account (8 weeks \pm 2 weeks from prior TACE cycle) and assessments (4 weeks \pm 1 week from last embolization in current cycle), and a 4 week (\pm 1 week) time between treatment of lobes of patients with bilobar disease, the assessment of objective response rate for patients with unilobar disease will be 15-25 weeks and 24-40 weeks for patients with bilobar HCC.

Patients whose response to treatment during the study makes them eligible for potentially curative therapies such as transplant, resection or percutaneous ablation will be offered those treatments, as appropriate in the decision of the treating physician. They will be discontinued from the treatment portion of the study and followed for survival per protocol.

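### The primary log-rank test uses none of the six baseline factors in the minimisation and so forgoes some power; the supportive Cox model also takes up covariates by baseline significance

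*Combined protocol and SAP*

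**What the plan says.** Section 6 (Randomization and Blinding) allocates by minimisation: "The adaptive model will control the balance of treatment groups within each site and also take into account the following baseline factors". The six factors are Child-Pugh stage, ECOG status, recurrent disease, AFP at a 400 ng/mL cut, macrovascular invasion and unilobar or bilobar disease. They are described as "baseline factors which will be weighted based on importance". The background section explains the poor prognosis of this disease by the fact that "liver cancer patients have underlying hepatic disease which can itself be fatal and can impact treatment options and response".

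Section 11.5.1 gives the primary comparison as follows: "Treatment groups will be compared on median survival using a log-rank test". It names no strata, no covariates and no hazard ratio. A multivariate Cox model on the ITT population includes site and every variable in the final minimisation, but of this model the plan says "This analysis will be considered supportive only". The same paragraph has the model also evaluate key baseline factors that turn out to differ significantly between the arms.

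Section 6 places unblinding at the lock of the treatment-phase database, after which "Unblinded survival data collection will continue until all patients have died or been lost to follow-up".

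**The concern.** Factors chosen and weighted for their importance are presumably thought to predict survival. A log-rank test that ignores prognostic factors draws less information from the same deaths than a Cox model that includes them. When allocation has been balanced on those factors, the unadjusted test is also conservative. The six factors must be recorded for every patient before randomization, so adjustment needs no new data. It would also supply an effect estimate, since the primary analysis specifies no hazard ratio.

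The second part is separate. Under randomization, a significant baseline difference is a chance event. A rule that takes up covariates on that basis selects on imbalance, not on prognosis, and leaves the model undefined until the arms have been compared. Because survival follow-up continues unblinded after the treatment-phase lock, the covariate list could be settled with allocations known.

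**Working it through.** **Inputs from the documents.** Two-sided 5%, 85% power, medians of 16 and 24 months, hazard ratio 1.5, 255 randomized per arm (Section 11.2). Analysis at 218 deaths or when the last patient reaches two years, whichever is first (Section 11.5.1). Six factors plus site in the minimisation (Section 6).

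**1. The plan's own figure.** Schoenfeld: deaths = 4(1.960 + 1.036)² / (ln 1.5)² = 218.45. Power at 218 deaths = Φ(√218 × ln 1.5 / 2 − 1.960) = Φ(1.033) = 84.9%. The plan's 218 and 85% are reproduced.

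At the planned medians, 24 months of follow-up on all 510 patients would give 255 × [(1 − 2^(−24/16)) + (1 − 2^(−24/24))] = 255 × 1.146 = 292 deaths, ignoring losses. The 218-death trigger is therefore the one to expect if the planning assumptions hold.

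**2. Simulation set-up.** The documents give no factor strengths, prevalences, accrual time or site numbers, so these are assumptions:
- 510 patients; minimisation with biased-coin probability 0.8 and equal weights on six binary factors and 30 unequal sites.
- Base prevalences 0.30, 0.50, 0.30, 0.25, 0.15 and 0.40. Patients were redrawn until they satisfied inclusion criterion 3e ("Patient MUST meet at least ONE of the following criteria": Child-Pugh B7, recurrent HCC or ECOG 1).
- Exponential survival, control median 16 months at average factor levels, uniform 36-month accrual, cut-off at the 218th death.
- The same hazard ratio for all six factors: 1.0, 1.3, 1.5 or 2.0.

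There were 6,000 trials per main power scenario and 20,000 per null scenario (SE 0.15 points). Setting (a) holds the treatment hazard ratio conditional on the factors at 1.5. Setting (b) holds the marginal hazard ratio near 1.5 (simulated mean 1.51).

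| Factor HR | (a) log-rank | (a) six-factor Cox | (a) gain, points | (b) log-rank | (b) Cox | Type I, log-rank | Type I, Cox |
|---|---|---|---|---|---|---|---|
| 1.0 | 84.2% | 84.5% | 0.3 | – | – | 5.1% | 5.3% |
| 1.3 | 82.8% | 84.4% | 1.6 | 86.1% | 87.2% | 4.7% | 5.4% |
| 1.5 | 81.1% | 84.4% | 3.4 | 86.2% | 89.4% | 4.3% | 5.3% |
| 2.0 | 73.0% | 84.2% | 11.2 | 87.3% | 94.4% | 3.5% | 5.4% |

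The gains in (a) have paired SEs of 0.2 to 0.4 points and were taken before rounding. In (a), the log-rank would need about 235 deaths at factor HR 1.5, and about 275 at 2.0, to match the adjusted test at 218.

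**3. Sensitivity in setting (a).**
- With 24-month accrual the gains are 1.4, 2.8 and 9.6 points at factor HR 1.3, 1.5 and 2.0.
- If only Child-Pugh and AFP are prognostic, the gain is 1.6 points at HR 1.5 each and 4.9 at HR 2.0 each.
- A second simulation with different prevalences and no site in the minimisation (2,000 trials per scenario) gave log-rank versus Cox power of 84.9 vs 85.1%, 83.7 vs 85.0%, 81.2 vs 85.4% and 72.1 vs 85.1% at factor HR 1.0, 1.3, 1.5 and 2.0. Adjusted type I error was 4.3 to 5.1%.
- A third, smaller run (about 1,500 trials per scenario) showed the same pattern, with adjusted type I error of 4.8 to 6.6%. The 6.6% comes from 1,445 trials, where one SE is √(0.05 × 0.95 / 1445) = 0.57 points.

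**4. How to adjust.** Adding 30 site strata to the six-factor model in (a) gives 79.9, 79.9, 78.7 and 77.8%, below the log-rank except at factor HR 2.0. Pooling sites with fewer than 10 patients gives 81.4, 81.0, 80.3 and 79.3%. With a between-site SD of 0.3 on the log hazard and factor HR 1.3 or 1.5, the log-rank has 81.1 and 79.2%, six factors 82.5 and 82.4%, and six factors plus site strata 79.3 and 79.3%. In the second simulation, a log-rank stratified on all 2⁶ = 64 cells fell to 75.0, 73.8, 73.1 and 71.8%.

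**5. The baseline-significance rule.** Section 11.4 names six characteristics outside the minimisation: the demographics ("Patient demographics (age, gender, race, ethnicity") and the number and size of target tumors. At 0.05 each, and taking them as independent, the chance that at least one qualifies by chance alone is 1 − 0.95⁶ = 26%.

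**The case against.** The strongest reply is that nothing falls short of the plan. Section 11.2 derives the hazard ratio from group medians, which are marginal quantities. Setting (b) is then the relevant one, and there the log-rank reaches 86 to 87%. This stands: the lower log-rank powers and the 235 or 275 deaths in (a) assume a smaller marginal effect than planned and are not shortfalls against the design. Even in (b), however, adjustment adds 1.1, 3.2 and 7.1 points.

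The gains also rest on assumed strengths. Eligibility is narrow (Child-Pugh no higher than 7, ECOG 0 or 1), so a hazard ratio of 2.0 on all six factors is an extreme case. The simulation fits the proportional-hazards form that generated the data, without missing values. These limits stand too. Part of the small gain is test size: raising alpha from 0.050 to 0.054 at 218 deaths adds about 0.8 points, roughly half the gain at factor HR 1.3.

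An adjusted model is already prespecified, and the remedy itself omits site from the primary model, so the argument cannot simply be to analyse as randomized. That is fair; the case is one of efficiency.

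The baseline-significance rule affects only a supportive analysis, and the text says such factors are evaluated, not that they must be retained. The 26% assumes that all six characteristics count as key, that the threshold is 0.05, and independence. None of this makes the rule a sound way to choose covariates.

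**Conclusion.** Both parts hold. The primary test is valid, with type I error at or below nominal within simulation error, and it is adequately powered for a marginal hazard ratio of 1.5. It nevertheless forgoes efficiency that the recorded baseline data could provide: about 1 to 4 points of power for weak to moderate factors, more than 10 only if all six are strong, and essentially none if they are not prognostic. These sizes depend on the assumed factor strengths, prevalences and accrual, and on the analysis taking place at 218 deaths. The objection to choosing covariates by baseline significance needs none of those assumptions. This is a worthwhile improvement, not the correction of an invalid analysis.

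**What to change.** Amend Section 11.5.1 before the treatment-phase database is locked and unblinded:

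- Make the primary test a two-sided 0.05 Cox score test of treatment, with the six minimisation factors listed by name as fixed covariates. Report the adjusted hazard ratio with its 95% confidence interval.
- Keep the unadjusted log-rank as a sensitivity analysis and the Kaplan-Meier medians for display.
- Do not stratify the primary model by individual site. Put site in a sensitivity model with its own pooling rule, because the existing rule for sites with fewer than 10 patients covers only the poolability analysis. Name treatment explicitly as a term.
- Delete the sentence on factors found to differ at baseline. If other covariates are wanted, name them now on prognostic grounds.

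The cost is an amendment; no new data are needed. The headline hazard ratio becomes conditional instead of marginal, the adjusted test ran slightly above nominal (5.3 to 5.4%) in the largest simulation, and the site model needs a rule of its own.
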